### **6.3 VISITS AT MONTHS 1 THROUGH 6 AND 8 (VISITS 3 THROUGH 9) DURING THE RANDOMIZED, TREATMENT PHASE**

All of the following should be performed or obtained at Visits 3 through 9, unless noted, within 3 days of the scheduled visit. For Visits 3 (Month 1), 4 (Month 2), and 7 (Month 5), Home

Protocol Amendment #3 version: 22 February 2016

*This protocol is solely for the purpose of communicating information about the investigational drug between Insmmed Incorporated and study personnel. Information is not to be reproduced, abstracted or used for sharing of information for any other purpose, whatsoever, except with the written permission of Insmmed Incorporated.*

Healthcare visits may be available for sites with IRB/EC approval to conduct Home Healthcare visits, and for qualifying subjects who may have difficulty attending clinic visits:

- administer SGRQ before study drug administration at the Months 3, 6, and 8 visits only (see [Section 7.3.1](#))
- administer EQ-5D-3L before study drug administration at the Months 3, 6, and 8 visits only (see [Section 7.3.2](#))
- collect information on healthcare resource utilization
- At Months 2, 4, 6, and 8 only: administer physical examination, including vital signs and pulse oximetry. Vital signs and pulse oximetry will be assessed both before and after study drug administration (see [Section 7.2.2](#) and [Section 7.2.3](#))
- administer 6MWT at the Months 4, 6 and 8 visits only (see [Section 7.2.1](#))
- administer the pulmonary function test at Month 6 only prior to study drug administration (see [Section 7.2.4](#))
- administer audiology test at the Months 3 and 6 visits only (see [Section 7.2.9](#))
- solicit concomitant medications (see [Section 7.2.8](#))
- assess AEs (see [Section 8](#))
- collect sputum specimen for microbiological assessment (see [Section 7.1.1](#))
- collect blood and urine specimens for clinical chemistry, hematology, and urinalysis testing at the Months 1, 3, 6, and 8 visits only and, for women of child-bearing, a urine pregnancy test at Months 1-6 and 8 (see [Section 7.2.7](#))
- collect blood (serum) and sputum specimen for biomarker assessment at the Month 6 visit only (CRP [c-reactive protein] and IL-6 [interleukin 6]) (see [Section 7.2.7](#))
- collect blood and sputum specimens for population PK sub-set analyses at the Months 1, 3, and 6 visits only (see [Section 7.4.1](#))
- collect sputum specimens for sputum-only PK sub-set analyses at the Months 4, 5 and 6 visits only, 2 days interruption of LAI dosing (see [Section 7.4.1](#))

Protocol Amendment #3 version: 22 February 2016

*This protocol is solely for the purpose of communicating information about the investigational drug between Insmmed Incorporated and study personnel. Information is not to be reproduced, abstracted or used for sharing of information for any other purpose, whatsoever, except with the written permission of Insmmed Incorporated.*

- collect blood (serum) and sputum specimens for Comprehensive PK Sub-Study analysis at the Month 1, 3 and 6 visits for Japanese subjects only (see [Section 7.4.3](#) and [APPENDIX 3](#))
- (Japan only) at Month 6 obtain CT chest scan as part of Japan specific CT Scan Sub-Study (see [APPENDIX 4](#))
- dispense sputum collection containers (see [Section 7.2.7](#))
- administer study drug at the study site (see [Section 5.3](#))
- dispense study drug
- collect previously dispensed study drug vials from subject.

Beginning with Month 3 and extending throughout the study, subjects will be assessed for culture conversion by the central microbiology laboratory ([Section 3.1](#)). Beginning with Month 4, relapse or recurrence will be assessed by the central microbiology laboratory ([Section 3.1](#)).

#### **6.4 MONTH 10 (VISIT 10) DURING THE RANDOMIZED, TREATMENT PHASE**

All of the following should be performed or obtained within 5 days of the scheduled visit:

- solicit concomitant medications (see [Section 7.2.8](#))
- assess AEs (see [Section 8](#))
- dispense study drug
- collect previously dispensed study drug vials from subject.

For subjects who were randomized to the multi-drug regimen only arm, this visit may take place as a telephone contact as no drug dispensation will be performed.

#### **6.5 MONTH 12 (VISIT 11) DURING THE RANDOMIZED, TREATMENT PHASE**

All of the following should be performed or obtained within 5 days of the scheduled visit:

Protocol Amendment #3 version: 22 February 2016

*This protocol is solely for the purpose of communicating information about the investigational drug between Insmmed Incorporated and study personnel. Information is not to be reproduced, abstracted or used for sharing of information for any other purpose, whatsoever, except with the written permission of Insmmed Incorporated.*

- administer SGRQ before study drug administration (see [Section 7.3.1](#))
- administer EQ-5D-3L before study drug administration (see [Section 7.3.2](#))
- collect information on healthcare resource utilization
- administer physical examination, including vital signs and pulse oximetry. Only vital signs and pulse oximetry will be assessed both before and after study drug administration (see [Section 7.2.2](#) and [Section 7.2.3](#))
- administer audiology test (see [Section 7.2.9](#))
- solicit concomitant medications (see [Section 7.2.8](#))
- assess AEs (see [Section 8](#))
- collect sputum specimen for microbiological assessment (see [Section 7.1.1](#))
- collect blood and urine specimens for clinical chemistry, hematology, and urinalysis testing and, for women of child-bearing, a urine pregnancy test (see [Section 7.2.7](#))
- (Japan only) obtain CT chest scan as part of Japan specific CT Scan Sub-Study (see [APPENDIX 4](#))
- dispense sputum collection containers (see [Section 7.2.7](#))
- administer study drug at the study site (see [Section 5.3](#))
- dispense study drug
- collect previously dispensed study drug vials from subject.

## 6.6 MONTH 14 (VISIT 12) DURING THE RANDOMIZED, TREATMENT PHASE

All of the following should be performed or obtained within 5 days of the scheduled visit:

- solicit concomitant medications (see [Section 7.2.8](#))
- assess AEs (see [Section 8](#))
- dispense study drug
- collect previously dispensed study drug vials from subject.

Protocol Amendment #3 version: 22 February 2016

*This protocol is solely for the purpose of communicating information about the investigational drug between Insmmed Incorporated and study personnel. Information is not to be reproduced, abstracted or used for sharing of information for any other purpose, whatsoever, except with the written permission of Insmmed Incorporated.*

For subjects who were randomized to the multi-drug regimen only arm, this visit may take place as a telephone contact as no drug dispensation will be performed.

## **6.7 END OF TREATMENT – UP TO MONTH 16 (VISIT 13) DURING THE RANDOMIZED, TREATMENT PHASE**

All of the following should be performed or obtained within 5 days of the scheduled visit:

- obtain 12-lead ECG (see [Section 7.2.5](#))
- administer SGRQ (see [Section 7.3.1](#))
- administer EQ-5D-3L (see [Section 7.3.2](#))
- collect information on healthcare resource utilization
- administer physical examination, including vital signs and pulse oximetry. (see [Section 7.2.2](#) and [Section 7.2.3](#))
- administer 6MWT (see [Section 7.2.1](#))
- administer audiology test (see [Section 7.2.9](#))
- obtain CT chest scan if part of CT Scan Sub-Study and no less than 6 months have elapsed since the previous CT scan was performed (see [Section 7.3.4](#), [APPENDIX 4](#))
- (Japan only) at Month 16, obtain CT chest scan as part of Japan specific CT Scan Sub-Study (see [APPENDIX 45](#))
- solicit concomitant medications (see [Section 7.2.8](#))
- assess AEs (see [Section 8](#))
- collect sputum specimen for microbiological assessment (see [Section 7.1.1](#))
- collect blood and urine specimens for clinical chemistry, hematology, and urinalysis testing and, for women of child-bearing, a urine pregnancy test (see [Section 7.2.7](#))
- collect blood (serum) specimen for biomarker assessment (CRP and IL-6) (see [Section 7.2.7](#))
- dispense sputum collection containers (see [Section 7.2.7](#))
- collect previously dispensed study drug vials from subject

Protocol Amendment #3 version: 22 February 2016

*This protocol is solely for the purpose of communicating information about the investigational drug between Insmmed Incorporated and study personnel. Information is not to be reproduced, abstracted or used for sharing of information for any other purpose, whatsoever, except with the written permission of Insmmed Incorporated.*

For subjects who do not convert, the last visit will occur no later than at the Month 8 visit. For subjects who do convert, the last visit will be at the visit corresponding to 12 months following their conversion dates. All subjects who discontinue study drug early should have all procedures listed in the end of treatment (EOT) visit performed, with the exception of the chest CT scan. A chest CT scan should only be performed if the subject is participating in the CT scan sub-study but only if 6 months or more have elapsed since the subject's last CT scan has been performed. Please refer to [APPENDIX 5](#) for Japan specific CT Scan Sub-Study study procedures and study schedule. High resolution CT scan is preferred, if available.

## **6.8 OFF-TREATMENT SAFETY FOLLOW-UP VISITS (VISIT 14, 15, AND 16) DURING THE OFF-TREATMENT PHASE FOR SUBJECTS WHO COMPLETE 12 MONTHS OF TREATMENT**

### Visit 14 (28 day off-treatment safety follow-up)

For any subject who completes treatment, all of the following should be performed or obtained within 5 days of the 28 day safety follow-up scheduled visit:

- solicit concomitant medications (see [Section 7.2.8](#))
- assess AEs (see [Section 8](#))
- dispense sputum collection containers (see [Section 7.2.7](#))
- collect sputum specimen for microbiological assessment (see [Section 7.1.1](#))
- collect sputum specimen for sputum-only PK assessment (see [Section 7.4.1](#))

### Visits 15 and 16 (3 and 6 months off-treatment safety follow-up)

All of the following should be performed or obtained within 7 days of the scheduled visit:

- administer SGRQ at the 3 month safety follow-up only (see [Section 7.3.1](#))
- administer EQ-5D-3L at the 3 month safety follow-up only (see [Section 7.3.2](#))
- administer physical examination, including vital signs and pulse oximetry at the 3 month safety follow-up only (see [Section 7.2.2](#) and [Section 7.2.3](#))

Protocol Amendment #3 version: 22 February 2016

*This protocol is solely for the purpose of communicating information about the investigational drug between Insmmed Incorporated and study personnel. Information is not to be reproduced, abstracted or used for sharing of information for any other purpose, whatsoever, except with the written permission of Insmmed Incorporated.*

- administer 6MWT at the 3 month safety follow-up only (see [Section 7.2.1](#))
- administer the pulmonary function test at the 6 month safety follow-up only (see [Section 7.2.4](#))
- solicit concomitant medications (see [Section 7.2.8](#))
- assess AEs (see [Section 8](#))
- dispense sputum collection containers (see [Section 7.2.7](#))
- collect sputum specimen for microbiological assessment (see [Section 7.1.1](#))
- collect sputum specimen for sputum-only PK assessment for the 3 month safety follow-up off-LAI only (see [Section 7.4.1](#))

## 6.9 END OF STUDY -12 MONTHS OFF-TREATMENT (VISIT 17)

All of the following should be performed or obtained within 7 days of the scheduled visit:

- administer physical examination, including vital signs and pulse oximetry (see [Section 7.2.2](#) and [Section 7.2.3](#))
- solicit concomitant medications (see [Section 7.2.8](#))
- assess AEs (see [Section 8](#))
- collect sputum specimen for microbiological assessment (see [Section 7.1.1](#))

The EOS visit is scheduled to occur 12 months after EOT and is for all subjects who complete 12 months of treatment from their first of 3 negative cultures that classified them as a converter.

## 7 STUDY VARIABLES AND METHODS OF ASSESSMENT

### 7.1 PRIMARY ENDPOINT VARIABLES

#### 7.1.1 Sputum Collection, Transport, and Assessment

Pre-dose expectorated or induced sputum specimens (approximately 3 mL) are required at Screening, Day 1, at Months 1 through 6, at Months 8 and 12, at EOT, at the 28 day, the 3, 6, and 12 months off-treatment visits. To improve the probability of obtaining a good sputum specimen, at least 2 and preferably 3 sputum samples will be obtained from each subject at each

Protocol Amendment #3 version: 22 February 2016

*This protocol is solely for the purpose of communicating information about the investigational drug between Insmid Incorporated and study personnel. Information is not to be reproduced, abstracted or used for sharing of information for any other purpose, whatsoever, except with the written permission of Insmid Incorporated.*

assessment. If a subject is unable to produce sputum spontaneously, one induced sputum specimen at the site will be acceptable. With the exception of the Screening samples (collected during the week following the Screening visit), each sputum sample will be collected on consecutive days prior to a scheduled visit. Subjects will refrain from administering LAI on the days sputum is obtained, starting 2 days prior to the scheduled visit, even if a spontaneous sputum cannot be obtained by the subject at home. At the scheduled visit, once sputum is collected (spontaneously or by induction), the administration of LAI can recommence. Sites are encouraged to notify subjects by telephone of this procedure 3 days prior to their scheduled visit. If a subject is unable to produce sputum independently, sputum may be induced as described in [APPENDIX 1](#), if these suggestions are safe for the subject. If a subject is still unable to produce sputum despite reasonable efforts, and they have already met the definition of converter, this will be recorded as a negative culture result at that time point.

Sterile, leak proof, non-wax, disposable plastic containers labeled with 2 subject identifiers will be used to collect specimens aseptically to avoid contamination. Sputum samples should be refrigerated, not frozen, until shipped to the central microbiology lab within 2 days of collection to avoid overgrowth by contaminating normal flora. No fixative or preservatives are to be used with sputum samples. Detailed instructions for collecting, processing, and shipping sputum specimens will be provided in the site laboratory manual.

Sites are strongly discouraged from performing local mycobacterium sputum cultures for the duration of the study, as this may introduce bias to subject assessments. Sputum may be sent to local laboratories to be cultured for organisms other than mycobacterium.

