Section 6 (multiple places in this section)	Added cross references to Appendix 5 for CT scans. Added activities in the Japan-specific CT Scan Substudy.  Changed Japanese to Comprehensive.  Changed cross reference for sputum collection containers from Section 7.2.7 to 7.1.1.  Changed 72 hours to 2 days interruption of LAI for the sputum-only PK substudy.	Request from Japan to have a CT Scan Substudy substantially different from the one for the rest of the world.  Request from Japan to change the title of the Japan-specific PK substudy. Corrected a previous error.  Sputum sample for PK will be collected at the clinic visit which is preceded by 2 days of a scheduled/planned interruption in LAI dosing for subjects randomized to LAI plus multi-drug per Section 7.1.1. The original intent of the protocol was for subjects to interrupt dose for 2 days as described. 72 hours assumes the subject takes the dose in the morning, have 2 days of interruption, and have their clinic visit in the morning of the next day (accounting for 72 hours). Since 72 hours was being misunderstood as 3 days, the protocol was revised to reflect 2 days of interruption as per original intention and per protocol. There is no change from 3 to 2 days.

Protocol Amendment #3 version: 22 February 2016

*This protocol is solely for the purpose of communicating information about the investigational drug between Inmed Incorporated and study personnel. Information is not to be reproduced, abstracted or used for sharing of information for any other purpose, whatsoever, except with the written permission of Inmed Incorporated.*

Confidential

	
Added “and sputum” and “in Japanese subjects only” for the bullet about the Japanese (now Comprehensive) PK Substudy.
 
Visit windows for Months 10, 12, 14, EOT, and 28-day safety follow-up were changed from <math>\pm 3</math> days to <math>\pm 5</math> days.
	
Sampling includes sputum as well as blood (serum). Clarified to the rest of the world that the Comprehensive PK Substudy applies only in Japan.
 
Change required for practical reasons related to scheduling visits.

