Section 6.3	
Added sentence on home healthcare visits for qualified subjects for Months 1, 2, and 5.
 
Removed physical examinations and vital signs at Months 1, 2, and 5
 
Added “and sputum” and specified only at Month 6 for biomarker samples.
 
Added “by the central microbiology laboratory” in regards to culture conversion assessment.
 
Deleted definitions of converter, relapse, and other details about assessing conversion, remaining in this study, or going to the separate open-label study.
	
Added the option for home health visits for Months 1, 2, and 5 for IRB/EC approved sites approved to conduct Home Healthcare visits, and for qualifying patients who may have difficulty attending clinic visits.
 
Physical examinations and vital signs no longer done at Months 1, 2, and 5.
 
Biomarkers are being assessed in sputum as well as serum.
 
Added to specify who makes the culture conversion assessment and to discourage sites from using local laboratories for this.
 
This information is provided in Section 3.1. Unnecessarily repeated information was deleted.

Section 6.7	
Removed administer study drug at the study site. Removed references to before or after study drug administration.
	
Study drug is not administered at the EOT visit.

Section 6.8	
Added “for subjects who complete 12 months of treatment” to the section heading.
 
Added dispense sputum collection containers to the 28-day, 3-month, and
	
Subjects who do not finish 12 months of treatment starting from the first of 3 negative cultures that defines culture conversion will not participate in the off-treatment phase.
 
Subjects are still collecting 3 sputum samples (2 at home on the 2 consecutive days before the clinic visit) per timepoint.

Protocol Amendment #3 version: 22 February 2016

*This protocol is solely for the purpose of communicating information about the investigational drug between Inmed Incorporated and study personnel. Information is not to be reproduced, abstracted or used for sharing of information for any other purpose, whatsoever, except with the written permission of Inmed Incorporated.*

Confidential

	6-month off treatment visits.	

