## 2.5 PHARMACOKINETIC OBJECTIVES

1. To evaluate the PK of LAI via a population PK approach (Months 1, 3 and 6).
2. To evaluate the concentration of amikacin in sputum after 2 days interruption of LAI dosing in a subset of subjects (Months 4, 5 and 6)
3. To evaluate the concentration of amikacin in sputum after 28 days off-LAI in a subset of subjects
4. To evaluate the concentration of amikacin in sputum after 3 months off-LAI in a subset of subjects

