## **5.5 SELECTION OF TIMING OF ADMINISTRATION**

Study drug may be administered QD around the same time each day, any time of day, in the fasted or as-fed condition.

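### The LAI hold starts on the first day of sputum collection, so home specimens cultured for the primary endpoint follow a shorter drug-free interval than the clinic specimen, and any carry-over would affect the LAI arm alone

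*Protocol*

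**What the plan says.** Section 7.1.1 of the protocol asks that "at least 2 and preferably 3 sputum samples will be obtained from each subject at each" assessment. Apart from the Screening samples, "each sputum sample will be collected on consecutive days prior to a scheduled visit". The Summary of Changes gives the split for the off-treatment visits: "Subjects are still collecting 3 sputum samples (2 at home on the 2 consecutive days before the clinic visit) per timepoint".

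The LAI hold is tied to the collection days: "Subjects will refrain from administering LAI on the days sputum is obtained, starting 2 days prior to the scheduled visit". LAI restarts at the visit, after sputum has been obtained.

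The protocol takes an interest in residual drug. Objective 2 of Section 2.5 is "To evaluate the concentration of amikacin in sputum after 2 days interruption of LAI dosing in a subset of subjects", at Months 4, 5 and 6. The Summary of Changes places that sample at the clinic: "Sputum sample for PK will be collected at the clinic visit which is preceded by 2 days of a scheduled/planned interruption in LAI dosing". Section 7.4.1 puts at least 60 LAI subjects in this subset. The population PK subset also has a pre-dose clinic sputum sample at Months 1, 3 and 6, in at least 16 US and 8 Japanese subjects.

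**The concern.** The hold begins on the day of the first home specimen. That specimen therefore has no full drug-free day before it, and the second has only one. Only the clinic specimen has two.

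If amikacin remaining in sputum suppresses growth, a still-infected LAI subject is more likely to have a negative month than an identical control subject, who has no LAI in any specimen. Central reading cannot correct a difference that is already in the specimen. The endpoints exposed are conversion by Month 6, which is primary, and time to conversion. The residual-drug measurement planned on treatment describes the specimen with the longest interval, so it cannot show whether the other two are affected.

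**Working it through.** **Plan's own figure.** Section 9.1: 5% versus 20%, 2:1 allocation (r = 2), 2-sided 0.05, 90% power, continuity-corrected chi-square. With d = 0.15 and pooled rate (0.05 + 2 × 0.20)/3 = 0.15:

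- uncorrected control n = [1.960√(3 × 0.15 × 0.85) + 1.282√(2 × 0.0475 + 0.16)]² / (2 × 0.0225) = 76.8
- corrected n = (76.8/4) × [1 + √(1 + 6/(2 × 76.8 × 0.15))]² = 86.5, so 87 control and 174 LAI, total 261

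This matches the protocol. The planned effect to compare against is 15 points.

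**Timing.** With no LAI on Day -2 or Day -1, the last dose is on Day -3. The amendment rationale counts the hours: "72 hours assumes the subject takes the dose in the morning, have 2 days of interruption, and have their clinic visit in the morning". Morning collection then gives about 24 h and 48 h (home) and 72 h (clinic). Section 5.5 does not fix the hour: "Study drug may be administered QD around the same time each day, any time of day". Evening dosing with morning collection gives about 12, 36 and 60 h.

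**Illustration of size.** The protocol gives neither specimen sensitivity nor any growth-suppression figure, so the following are assumptions: three independent specimens per visit, a visit positive if any specimen is positive, no true treatment effect, and an unaffected clinic specimen. Let s be per-specimen sensitivity in a still-infected subject, and q24 and q48 the proportions of otherwise positive home specimens that are suppressed.

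- Monthly miss probability, control: m = (1 − s)³
- Monthly miss probability, LAI: m = (1 − s)(1 − s(1 − q24))(1 − s(1 − q48))
- Chance of 3 consecutive negatives in Months 1 to 6: m³[1 + 3(1 − m)]

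Example, s = 0.6, q24 = 0.8, q48 = 0.5: m = 0.4 × 0.88 × 0.70 = 0.2464, and 0.2464³ × [1 + 3 × 0.7536] = 4.88%.

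| s | Control | LAI, q = 0.5 / 0.25 | LAI, q = 0.8 / 0.5 |
|---|---|---|---|
| 0.5 | 0.71% | 4.24% | 11.48% |
| 0.6 | 0.10% | 1.29% | 4.88% |
| 0.8 | 0.00% | 0.04% | 0.38% |

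**Which s is plausible.** Section 1.1.3 reports 6.7% negative sputum at Day 84 in the placebo arm of the earlier NTM study. If all of those were false negatives from three specimens, (1 − s)³ = 0.067 and s is about 0.59. True conversions among them, or fewer specimens per visit, would make s higher. At s = 0.59 the two scenarios give about 1.4% and 5.2%, against 0.1% in control. By contrast, s = 0.5 would imply 0.5³ = 12.5% negative visits among infected controls.

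**Effect on the test.** Take 5% true conversion in both arms, 174 versus 87 subjects and the continuity-corrected chi-square, by exact enumeration. The chance of a significant result favouring LAI is 0.6% with no bias. It is 3.3% if 2% of LAI non-converters are falsely converted, and 15.2% if 5% are (observed LAI rate 0.05 + 0.95 × 0.05 = 9.75%).

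**The case against.** **The clinic specimen is protected.** Section 7.1.1 lets LAI restart only once sputum has been collected at the visit, accepts a single induced specimen at the site, and foresees that home sputum may be missing. Appendix 1 requires induction at clinic visits when the subject cannot expectorate enough. A reader might infer from the two-specimen minimum that a month is often decided on home specimens alone. The documents do not support that; it would need clinic induction to fail. Under an any-positive rule, visit sensitivity cannot fall below that of the clinic specimen. This stands, although the protocol does not state the combination rule, which may be in the SAP.

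**The large figures are unsupported.** A reader might take the 11% cell as the likely size. It needs s = 0.5, which fits poorly with the 6.7% above, though that is one estimate from a small study and excludes nothing firmly. If home specimens were wholly uninformative, the LAI figure would be 17.9% at s = 0.6 and 2.7% at s = 0.8. No document supports complete suppression, or indeed any suppression rate.

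**A 24 h sputum assay exists.** The Comprehensive PK Sub-Study in Japan assays sputum 24 h after dosing on Day 1. That is after a first dose, in about 8 subjects, and is not a cultured home specimen. It limits what can be said about missing measurements but does not fill the gap.

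**Other checks exist.** Cultures use agar and liquid media. Converters who complete treatment are cultured again at 28 days and at 3, 6 and 12 months off treatment, and durability at 3 months is a secondary endpoint. These could expose conversions that were only residual drug, but Section 9.4 makes the Month 6 analysis final before the study is complete.

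**Supportive analyses belong in the SAP, and drug neutralisation in the laboratory manual.** Either may already deal with this. The collection rule and the PK sampling are nevertheless fixed in the protocol, and an SAP cannot recover dose-to-specimen intervals that were not recorded.

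**Conclusion.** The point holds as a possible one-sided ascertainment bias on the primary endpoint and on time to conversion. The unequal drug-free intervals follow directly from Section 7.1.1, and so does the direction of any carry-over. Whether carry-over occurs, and how much, cannot be learned from the protocol. Under the stated assumptions the excess false conversion in the LAI arm is near 0 at s = 0.8 and about 1 to 5 percentage points at s = 0.6, against a planned 15. It would be wrong to read this as evidence that the primary result is inflated. It is an open question that the trial could answer from cultures it already makes, and the upper part of the range is large enough to disturb the primary test.

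**What to change.** 1. Record, for each cultured specimen, the collection day and the date of the last LAI dose. Appendix 1 already puts collection date and time on container labels, so the main addition is the dose date.
2. Add to Section 9.6.1 a supportive analysis of conversion by Month 6 using only the clinic-visit specimen in both arms. The number of specimens is then equal, and every LAI specimen has the full interruption.
3. Add a by-arm table of within-visit home versus clinic results. An excess of home-negative, clinic-positive visits over the reverse, in the LAI arm but not in control, would be the sign of carry-over. The control arm allows for ordinary differences between home and clinic collection.

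The cost is one data field and some analysis wording; no extra cultures are needed. The downside is that one specimen per visit detects less in both arms. With m = 1 − s, false conversion in still-infected subjects is 17.9% at s = 0.6 and 2.7% at s = 0.8, equally in each arm if the clinic specimen is unaffected. The analysis therefore supports the primary one and does not replace it. It also cannot rule out residual drug in the clinic specimen, which the PK subsets address.

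Assaying amikacin in home aliquots is an optional extra, not part of the fix. Microbiology sputum is kept refrigerated and unfrozen while PK samples are stored at or below −20°C, so specimens would have to be split. No change to dosing is proposed.
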